#### 3.2 Secondary Outcome Measures

1. [For Secondary Objectives 1 and 3] HCV RNA <LLOQ (TD or TND) at study visits, using the visit windows as defined in Protocol Section 6.0.
2. [For Secondary Objective 2] Virologic failure, defined as failure to achieve unquantifiable HCV RNA and confirmed increase in HCV RNA  $>1 \log_{10}$  from on-treatment nadir.

Outcomes at study visits after Week 28 will be obtained after the primary completion date (PCD) and will be addressed in a separate analysis plan. For the outcome measures obtained after PCD, the results will be posted to ClinicalTrials.gov after the initial results submission and no later than one year after the last participant's study completion.

## 4 Statistical Principles

### 4.1 General Considerations

- The analysis will include all participants who initiate the study treatment.
- Baseline refers to study evaluation closest to Week 0 prior to initiation of study treatment.
- For summaries of outcomes at specified study visits (e.g. HCV RNA at study visits for Secondary Outcome Measure 1), study visit windows as specified in Protocol Section 6.0 will be used, unless specified otherwise. In the event of multiple results within a study window, the result closest to the scheduled evaluation week based on the time since study entry randomization date will be used.
- Continuous variables will be summarized with min, Q1, median, Q3, and max, unless specified otherwise. Mean and standard deviation may also be reported, if there are sufficient numbers to make these statistics meaningful.

### 4.2 Analysis Approaches

- For the primary analysis:
  - As described in Section 3.1 above on Primary Outcome Measures, if a participant does not have any HCV RNA measurements in the SVR12 visit window, then the participant will be considered SVR12 failure, unless there are preceding and subsequent HCV RNA measurements that are both LLOQ (either TD or TND). The latest available preceding and the earliest available subsequent HCV RNA measurements around the targeted SVR12 visit window will be used. **If the participant's visit schedule was affected by COVID-19 as outlined in CM #2 and (1) only one HCV RNA sample is available after the study treatment, and (2) the sample is collected after the SVR12 visit window, then this result will be used as the primary outcome.**
  - Otherwise, not achieving unquantifiable HCV RNA at the study visit corresponding to the SVR12 evaluation will be considered failure for SVR12 determination in the primary analysis regardless of the reason. As such, early discontinuation of the study prior to the SVR12 visit and reinfection prior to the SVR12 visit will be considered a failure.
  - For the SVR12 analysis, a supplementary analysis will be conducted in the analysis set that excludes (1) participants who discontinued the study for reasons not related to the study treatment, and (2) participants who became re-infected with HCV prior to SVR12 visit. Reasons not related to study treatment may include, but are not limited to: participant moved away, participant cannot get to the clinic, participant cannot be located.
- All available data for the indicated study visits from the participants who initiate the study treatment will be used in the analysis, and the number of participants with available data will be specified for each analysis.
- Confidence intervals around proportions will be provided using the Wilson method for binomial data.

- Subgroup analyses based on the screening HIV infection status will be conducted for the HCV RNA analyses to address Secondary Objective 3.

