### 1.2 Version History

- Version 1.0 was developed based on Protocol Version 1.0, dated June 07, 2019.
- No changes after review of Protocol Version 1.0, Letter of Amendment #1, dated December 18, 2019.
- Changes due to the study visits affected by COVID-19 outlined in CM #2, dated April 20, 2020. Changes were made in Section 2.5 (HCV interim monitoring), Section 3.1.1 (about primary outcome on SVR12 HCV RNA), Section 3.1.2 (clarification of timeframe) and Section 4.2 first bullet (about HCV RNA data for SVR12 analysis). Typos in 3.1 after asterisk were also corrected. Changes from Version 1.0 are in **bold text**.
- No changes after review of Protocol Version 1.0, Letter of Amendment #2, dated August 14, 2020.
- No changes after review of Protocol Version 1.0, Letter of Amendment #3, dated September 9, 2020.
- No changes after review of Protocol Version 1.0, Letter of Amendment #4, dated October 13, 2020.

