### 3 Outcome Measures

#### 3.1 Primary Outcome Measures

1. [For Primary Objective 1] SVR12 defined as achieving unquantifiable HCV RNA (<LLOQ TD or TND) at the study visit occurring at 12 weeks after treatment discontinuation (week 16). The sample within the visit window for week 12, as defined in Protocol V1.0 Section 6.0, will be used. If a participant does not have any HCV RNA measurements in this time period, then the participant will be considered as SVR12 failure, unless there are preceding and subsequent HCV RNA measurements\* that are both LLOQ (either TD or TND), **or the participants' visit schedule was affected by COVID-19 as outlined in CM #2.**
2. [For Safety in Primary Objective 2] Any reported AE occurring after initiation of study treatment through 4 weeks after the treatment **discontinuation.**
3. [For Tolerability in Primary Objective 2] Tolerability, defined as completion of 4 weeks of treatment without discontinuation due to AEs.

\* The scheduled HCV RNA visits that may be used for the SVR12 determination in case of the missed measurement in the **Week 16** visit window are weeks 8, 12 and 28.

Unscheduled HCV RNA visits may also be used, if applicable. See Section 4.2 below on the analysis approach to SVR12.

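### SAP 4.2 scores one late unquantifiable sample as SVR12 success but two as failure; SAP 3.1 omits 4.2's conditions and cites the unamended week 16 window

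*SAP*

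**What the plan says.** **SAP 3.1, item 1.** The window is fixed by reference: "The sample within the visit window for week 12, as defined in Protocol V1.0 Section 6.0, will be used". A participant with no HCV RNA result in it is a failure, with two exceptions. One is bracketing by unquantifiable results. The other is that the participant's "visit schedule was affected by COVID-19 as outlined in CM #2". This second exception has no sample condition and names no replacement outcome. The section closes with "See Section 4.2 below on the analysis approach to SVR12".

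**SAP 4.2, first bullet.** Bracketing is kept: "The latest available preceding and the earliest available subsequent HCV RNA measurements around the targeted SVR12 visit window will be used". For participants affected under CM #2, the late result becomes the primary outcome if "only one HCV RNA sample is available after the study treatment, and (2) the sample is collected after the SVR12 visit window". Everything else falls to the default: "Otherwise, not achieving unquantifiable HCV RNA at the study visit corresponding to the SVR12 evaluation will be considered failure".

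**Population.** SAP 4.1: "The analysis will include all participants who initiate the study treatment".

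**Week 16 window.** Protocol V1.0 Section 6.2.3 gives -5/+21 days, CM #2 gives -14/+42 and LOA #3 gives -5/+42. SAP 1.2 records "No changes after review of Protocol Version 1.0, Letter of Amendment #3, dated September 9, 2020".

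**Scope.** CM #2 concerns the 10 participants enrolled by 18 March 2020. Its change to Section 6.3.10 (NOTE A) restricts their Step 1 HCV RNA testing to the week 16 visit.

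**The concern.** These sentences score the primary endpoint. Three things are wrong with them.

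- 3.1 and 4.2 do not have the same scope. 3.1 exempts every CM #2-affected participant who lacks an in-window sample. 4.2 rescues only two sample patterns.
- The single-sample condition in 4.2 makes the score depend on how many late samples exist, not on what they show. A second unquantifiable late sample is further evidence of cure, yet it turns a success into a failure.
- The cited window is not the one sites were told to use. Read literally, a sample that complied with the memo or letter in force can fall outside it.

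The success criterion needs 40 of 44, so a single score can decide whether it is met.

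**Working it through.** **1. Scoring by sample pattern.** Take a CM #2-affected participant with no in-window sample.

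| Post-treatment samples | SAP 3.1 | SAP 4.2 |
|---|---|---|
| Below LLOQ both before and after the window | not a failure | success (bracketed) |
| One, after the window, below LLOQ | exempt | success |
| Two, both after the window, both below LLOQ, none earlier | exempt | failure |
| One, before the window, below LLOQ | exempt | failure |
| None | exempt, no outcome given | failure |

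Row 2 is not an automatic success. The rule uses the result, so a quantifiable late sample is a failure. Rows 2 and 3 show the fault inside 4.2. Rows 3 to 5 show where 3.1 is wider than 4.2.

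**2. Windows in days after last dose.** Twelve weeks is 84 days.

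- V1.0: 84 - 5 = 79 to 84 + 21 = 105
- CM #2: 84 - 14 = 70 to 84 + 42 = 126
- LOA #3: 84 - 5 = 79 to 84 + 42 = 126

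Two bands change status with the window used:

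- *Days 106 to 126 (+22 to +42).* In window under CM #2 and LOA #3, but late under V1.0. An unquantifiable sample here, with no earlier unquantifiable one to bracket it, is a failure on the literal V1.0 reading. The exception is a CM #2 participant for whom it is the only post-treatment sample. This band is not confined to the 10, because LOA #3 keeps +42 when accrual reopens and allows virtual visits at other time points.
- *Days 70 to 78 (-14 to -6).* Allowed by CM #2, but before the window under V1.0 and LOA #3. The 4.2 rescue covers only samples after the window. Such a sample is therefore a failure unless a later unquantifiable one brackets it, and CM #2 does not require an in-person week 28 visit once week 16 has been done.

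**3. Effect of one participant.** Inputs from Protocol 10.4 and SAP 2.4: n = 44, threshold 80%, assumed true SVR12 95%, Wilson two-sided 90% interval, z = 1.645.

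Lower limit = [p + z²/(2n) - z·√(p(1-p)/n + z²/(4n²))] / (1 + z²/n)

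- 40/44: interval 81.2% to 95.9%, met
- 39/44: interval 78.4% to 94.4%, not met

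Both reproduce Protocol Table 10.4-2. The exact probability of 40 or more out of 44 is 0.933 at 95%, matching the stated 93%, and 0.044 at 80%.

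If exactly one participant's score is in doubt, it decides the result only when the other 43 include exactly 39 successes. P(Bin(43, p) = 39) is 0.104 at p = 0.95, 0.203 at 0.90 and 0.030 at 0.97. These figures are conditional on a case existing.

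**The case against.** The strongest reply is that 4.2 plainly governs. 3.1 refers to it, and SAP Section 5 item 9a computes the primary result by it. Its closing default gives every pattern a score. This stands: the documents do have an operative rule, and 3.1 is loose drafting rather than a rival rule. It does not cure the single-sample condition, which is inside 4.2.

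Second, two late samples with none earlier should be rare. NOTE A makes one sample the expected case, and CM #2 directs a participant who missed week 16 to an in-person week 28 visit, which the single-late-sample rule fits. This also stands.

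Third, the reference to V1.0 can mean V1.0 as amended. The memo and letters are all issued against Version 1.0, and LOA #3 says that the extended upper bound remains. That is a fair reading and would settle days 106 to 126. It would not settle days 70 to 78, because CM #2 and LOA #3 give different lower bounds.

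Fourth, the SMC reviewed the first 10 on 17 August 2020, and SAP 2.5 had set that review for when their SVR12 results were available. This suggests few or no missing results. It is not proof, since no sample dates are given.

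Finally, pattern-level coding may be in the Analysis Implementation Plan, which is not among the documents. The SAP should still define its own primary endpoint consistently.

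**Conclusion.** The point holds as a minor one. 3.1 states the COVID-19 exception without 4.2's conditions. The single-sample condition in 4.2 gives a perverse score for one pattern. The window citation leaves two bands of sample dates open to different scoring.

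Exposure to the 4.2 fault and to the lower-bound question is at most 10 participants. The number actually affected is not in the documents and may be zero. The upper-bound question could reach later enrollees, but only on the literal V1.0 reading. One score separates 40/44 from 39/44, as it would for any scoring question in this trial.

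A reader might infer that 3.1's exemption lets a participant without any sample be left out, so that a smaller denominator turns a missed criterion into a met one. The documents do not support that. SAP 4.1 and Protocol 10.1 and 10.6 include everyone who starts treatment, and the only analysis set with exclusions is the supplementary one. Nor do they support inferring that a cure has already been misclassified, because no affected case is shown.

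**What to change.** 1. In SAP 3.1, make the COVID-19 exception apply only under the conditions set out in Section 4.2.
2. In SAP 4.2, for CM #2-affected participants, replace the single-sample condition: if there is no in-window and no earlier post-treatment sample, the earliest post-window result is the outcome. Keep the bracketing rule, and keep failure for a participant with no post-treatment sample.
3. Cite the week 16 window as Section 6.0 as amended by CM #2 and LOA #3, and name the lower bound used for the CM #2 participants.
4. Record that the change was made after the SMC review of 17 August 2020, and show scoring under the current text as a sensitivity analysis.

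The cost is a few sentences and one table, with no new data. The drawback is a change to primary scoring in an open-label trial after the affected participants have been reviewed. Item 4 discloses it and lets a reader see whether it alters anything.

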## A Phase II Trial of Glecaprevir/Pibrentasvir Fixed-dose Combination Treatment for Acute Hepatitis C Virus Infection (PURGE-C)

DESIGN

This is a phase II single-arm, open-label study to assess the efficacy of a fixed dose combination (FDC) of glecaprevir/pibrentasvir (G/P) given for 4 weeks in acute hepatitis C (HCV)-infected participants, with and without HIV-1 coinfection.

The study has two steps:

Step 1: Four weeks of treatment for acute HCV infection and up to 24 weeks of follow-up. Post-treatment follow-up visits in Step 1 will occur at 4, 8, 12, and 24 weeks after the end of study treatment (G/P). Participants with HCV recurrence (reinfection, suspected relapse or undefined post-treatment viremia) or HCV virologic failure before or at the week 16/SVR12 (sustained virologic response 12 weeks post-treatment) visit during Step 1 will be eligible for re-treatment (Step 2).

Step 2: Re-treatment will be with G/P with or without ribavirin (RBV) for up to 16 weeks. Post-treatment follow-up for Step 2 will include visits for SVR12 determination.

DURATION

Up to 28 weeks in Step 1: 4 weeks on treatment and 24 weeks of post-treatment follow-up.

Up to 40 weeks in Step 2: up to 16 weeks of re-treatment and up to 24 weeks of post-treatment follow-up.

SAMPLE SIZE

Minimum of 44 participants, including at least 10 participants living with HIV-1 co-infection. If a participant discontinues early for reasons unrelated to study treatment and is not evaluable for SVR12 while registration is ongoing, then an additional participant may be enrolled as determined by the study team to attain an adequate number for key supporting analysis on SVR12. Additional enrollment may occur more than once, up to maximum enrollment of 50 participants.

POPULATION

Men and women age  $\geq 18$  years with acute HCV-infection (may be first HCV infection or re-infection) of any genotype, living with or without HIV-1 co-infection.

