regardless of the reason, and re-infection prior to the SVR12 visit will also be considered a failure. Understanding reasons for SVR failure is important, and reasons for SVR failure will be described for the anticipated small number of non-SVRs. In addition, an important secondary analysis will be an SVR12 analysis that excludes participants who discontinue the study prior to the SVR12 evaluation for reasons clearly not related to study treatment and participants who become re-infected prior to when SVR12 can be assessed. Reasons for discontinuation unrelated to study treatment may include: participant moved away, participant cannot get to the clinic, participant cannot be located. To ensure that the study is well-powered for this important secondary analysis, additional participants may be enrolled if the study is still enrolling participants when the team becomes aware of such early study discontinuations. The maximum replacement number will be 6 for the study, so that study enrollment will not be greater than 50.

The primary outcome at 12 weeks after treatment discontinuation (week 16) may be evaluated for each participant prior to the completion of study. The primary analysis timeline will be driven by the last participant's completion of the primary outcome visit, rather than the study completion date. Results from the primary analysis on SVR12 may be presented publicly, for example at a conference, when the data related to such analysis are complete, prior to study database finalization.

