### 10.6 Analyses

The primary efficacy objective will be addressed by estimating the proportion of participants who achieve SVR12 ([section 10.2.1.1](#) describes this primary endpoint). All enrolled participants who receive any study treatment will be included in the primary analysis. A two-sided 90% CI will be calculated around the estimated SVR12 proportion using the Wilson method for binomial data. If this CI is entirely above 80%, then it will be concluded that there is evidence that the underlying SVR12 proportion is greater than 80%.

For the primary safety analysis, the AEs occurring after initiation of study treatment through the study visit occurring 4 weeks after the treatment completion will be summarized. The proportion of study participants with AEs will be estimated with a two-sided 95% CI around the estimate. As a secondary analysis, all reported AEs (which include events that occur after the time frame defined for the primary safety analysis) will be summarized. A two-sided 95% CI will also be provided for the proportion of study participants with AEs. The Wilson method will be used.

As a secondary analysis, SVR12 will be assessed in the analysis set that excludes participants who discontinued the study early for reasons clearly not related to the study

treatment and participants who became re-infected with HCV prior to SVR12 visit. Reasons not related to study treatment include: participant moved away, participant cannot get to the clinic, participant cannot be located. The analysis will use methods similar to the primary analysis. SVR12 results will also be described separately by HIV-1 infection status.

The secondary HCV RNA endpoints (HCV RNA <LLOQ at study visits) will also be assessed with proportion estimates with two-sided 90% CI using the Wilson method, similar to the primary efficacy analysis on SVR12.

Tolerability failures and virologic failures, as defined in [section 10.2.2](#), will be listed and described. A tolerability failure listing will be accompanied by treatment duration and the associated AE(s). Listings on virologic failure will be accompanied by HCV RNA results and any available information on HCV genotype/subtype, RAS and phylogenetic results.

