- b. As a supplementary analysis, SVR12 will be assessed in the analysis set that excludes participants who discontinued the study early for reasons clearly not related to the study treatment and participants who became re-infected with HCV prior to SVR12 visit, as described in Section 4.2.
10. Analysis of Primary Outcome Measure 2 described in Section 3.1
- a. To address safety in Primary Objective 2 described in Section 2.3.1, the AEs occurring after initiation of study treatment through the study visit occurring 4 weeks after the treatment completion will be summarized. The proportion of study participants with AEs will be estimated with a two-sided 95% CI around the estimate.
  - b. As a supplementary safety analysis, all reported AEs (which include events that occur after the time frame defined above for Primary) will be summarized. A two-sided 95% CI will also be provided for the proportion of study participants with AEs.
11. Analysis of Primary Outcome Measure 3 described in Section 3.1
- a. To address tolerability in Primary Objective 2 described in Section 2.3.1, tolerability failures will be listed and described.
  - b. The tolerability failure listing will be accompanied by treatment duration and the associated AEs.
12. Analysis of secondary outcome measures
- a. To address Secondary Objective 1, HCV RNA measurements at study visits will be assessed with proportion estimates with two-sided 90% CI.
  - b. To address Secondary Objective 2, virologic failures will be listed and described. Listings on virologic failure will be accompanied by HCV RNA results and any available information on HCV genotype/subtype, RAS and phylogenetic results.
  - c. To address Secondary Objective 3, SVR12 analysis described above in 9.a will be presented separately by HIV-1 infection status. In addition, HCV RNA measurements at study visits described above will be assessed with proportion estimates with two-sided 90% CI for the subgroup consisting of HIV-1 infected participants.

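### SAP 4.2 drops the protocol's time limit from the first exclusion of the supplementary SVR12 set, so its literal text removes participants whose SVR12 result is known

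*SAP*

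**What the plan says.** The set is described in four places, in three different ways.

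- **Protocol 10.1** "excludes participants who discontinue the study prior to the SVR12 evaluation for reasons clearly not related to study treatment". It has both a time limit and the qualifier that the reason be clearly unrelated.
- **SAP 4.2**, limb (1), "excludes (1) participants who discontinued the study for reasons not related to the study treatment". It has neither. Limb (2) of the same sentence reads "2) participants who became re-infected with HCV prior to SVR12 visit", so the only time limit in the sentence is attached to re-infection.
- **SAP section 5, item 9b**, "excludes participants who discontinued the study early for reasons clearly not related to the study treatment", and then points back to 4.2 for the description.
- **Protocol 10.6** "excludes participants who discontinued the study early for reasons clearly not related to the study" treatment. Like item 9b, it has the qualifier and a reference to leaving early, but no SVR12 limit.

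The protocol gives this analysis weight. Section 10.1 says: "To ensure that the study is well-powered for this important secondary analysis, additional participants may be enrolled", with at most 6 replacements and a ceiling of 50. The Schema reserves replacement for a participant who "discontinues early for reasons unrelated to study treatment and is not evaluable for SVR12".

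**The concern.** SVR12 is read at week 16. Participants who do not enter Step 2 are followed to week 28, and those who do are followed for 12 weeks after re-treatment, or 24 if ribavirin was given (Protocol 6.2.5). A participant can therefore have a known SVR12 result and then move away or be lost. Limb (1) as written excludes that person. This includes a known Step 1 failure who leaves during Step 2 before the data lock.

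Three things would be at stake in the supplementary analysis:

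- Known outcomes would be discarded in an analysis meant to set aside unknown ones.
- Those participants would not be replaced, because replacement is for people who cannot be evaluated for SVR12.
- Removing a Step 2 leaver whose recurrence was not re-infection removes a failure, which can only raise the estimate. Limb (2) already removes the re-infections.

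**Working it through.** **1. The plan's own figures.** Inputs from Protocol 10.4 and 10.6: N = 44, threshold 80%, two-sided 90% Wilson interval (z = 1.645, z² = 2.706), assumed true SVR12 95%. The lower bound is

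[p + z²/(2n) − z·√(p(1−p)/n + z²/(4n²))] / (1 + z²/n), with p = x/n.

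For 40/44 the centre is 0.885 and the half-width 0.073, so the lower bound is 81.2%. For 39/44 the centre is 0.864 and the half-width 0.080, so it is 78.4%. Both agree with Table 10.4-2, and 40 is the smallest count that clears 80%. The exact binomial chance of 40 or more out of 44 at 95% is 93.3% (Table 10.4-1: 93%).

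**2. One participant removed after the SVR12 result is known.** The 80% line is only a yardstick here, since item 9b sets no decision rule.

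| Removed | Before | Lower bound | After | Lower bound |
|---|---|---|---|---|
| 1 failure | 39/44 | 78.4% | 39/43 | 80.8% |
| 1 failure | 44/50 | 78.4% | 44/49 | 80.5% |
| 1 success | 43/48 | 80.1% | 42/47 | 79.7% |
| 1 success | 40/44 | 81.2% | 39/43 | 80.8% |

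The first three rows cross 80% and the fourth does not. From 40/44, three known successes must go before the bound falls below 80% (37/41, 79.96%). All these examples lie near the cut-off.

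**3. Loss after week 16 that is equal for successes and failures.** The documents give no such rate, so the rates below are assumed. N = 44 with known results, true SVR12 95%, and each participant independently lost with probability l.

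| l | Expected N | Mean estimate | Chance bound > 80% | Mean CI width |
|---|---|---|---|---|
| 0 | 44 | 95.0% | 93.3% | 11.3 points |
| 5% | 41.8 | 95.0% | 90.9% | 11.6 |
| 10% | 39.6 | 95.0% | 88.1% | 11.9 |
| 20% | 35.2 | 95.0% | 84.6% | 12.8 |

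Equal loss causes no bias. The fall in the fourth column is partly binomial discreteness. At fixed N the chance is 93.3% at 44, 93.8% at 43, 94.3% at 42 and 85.3% at 41, because the number of failures allowed is 4 from 42 to 44 and 3 at 41. The steady cost is the wider interval.

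**4. With the limit restored,** nobody with a known SVR12 result is removed. N = 44, the 40/44 cut-off and the 93% power are unchanged.

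**The case against.** The best answer is that the context already supplies the limit. Just before limb (1), SAP 4.2 says that "early discontinuation of the study prior to the SVR12 visit and reinfection prior to the SVR12 visit will be considered a failure". The two limbs take up the same two groups in the same order. Protocol 10.1 is explicit, the Schema ties replacement to evaluability, and the SAP version history records no change to this set. An analyst who reads all of this would probably build the narrower set, and the Analysis Implementation Plan, which is not among the documents, may say so.

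Most of that stands as evidence of intent, but it does not cure the text. The sentence before limb (1) defines failures in the primary analysis, not the supplementary set. Leaving at week 20 is still early against a final visit at week 28, so item 9b does not exclude it, and item 9b sends the reader back to 4.2.

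A reader might also infer more than the documents support:

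- **That such leavers will be in the data.** They may be. SAP 1.1 finalizes the analysis after the last week 28 visit, and item 5a lists premature study discontinuations without a time limit, so they could be recorded. No rate is given. Letter of Amendment #4 allows Step 2 entry up to 270 days after the confirmatory sample, so some Step 2 departures may fall after the lock.
- **That power falls steadily with each loss.** It does not. Going from 44 to 43 or 42 raises it slightly.
- **That the estimate is biased upward.** The direction depends on who leaves.

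**Conclusion.** The point holds as a conflict between the SAP's stated rule and Protocol 10.1, and it is worth correcting. It does not reach the primary analysis or its 80% conclusion, and the documents do not support reading it as a threat to either. Everyone who starts treatment stays in that analysis.

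The effect is confined to the supplementary SVR12 estimate. Its size cannot be predicted without a rate of leaving after week 16. Near the cut-off, one removal can take the lower bound across 80% in either direction. If loss is unrelated to outcome, the cost at 5% to 20% assumed loss is an interval 0.3 to 1.5 points wider (11.6 − 11.3 and 12.8 − 11.3), with no shift in the mean. Confidence is high on the wording gap and low on its practical effect, since the narrower set was probably intended.

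**What to change.** Change the SAP only. In 4.2, limit exclusion (1) to participants who left the study before the SVR12 evaluation for reasons clearly unrelated to study treatment, and use the same phrase in item 9b. Add that no participant with an SVR12 result is excluded because of later discontinuation, including in Step 2. A result here means one that was observed, or that was assigned by the rule using preceding and subsequent measurements or by the COVID-19 rule. Protocol 10.6 needs no amendment, because 10.1 already carries the limit.

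The restored definition still excludes a participant with confirmed, non-re-infection failure who leaves before the SVR12 evaluation for an unrelated reason. As an option, a sensitivity analysis could keep as failures those with confirmed virologic failure, or confirmed recurrence not classified as re-infection, before leaving. It should state its own possible downward bias. With 10% unrelated loss and every failure visible before leaving, a true 80% would be estimated at 0.80 × 0.90 / (0.80 × 0.90 + 0.20) = 0.72/0.92 = 78.3%.

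The cost is one or two sentences and no new data. The downside is that the supplementary estimate may be slightly less favourable when a known failure who later leaves is kept.
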